#### **10.5.3.2 Adverse events**

Summary tables for AE will include only AE that started or worsened during the on-treatment period, the treatment-emergent AE.

The incidence of treatment-emergent adverse events (new or worsening from baseline) will be summarized by system organ class and or preferred term, severity (based on CTCAE v5 grades), type of adverse event, and relation to study treatment

Serious adverse events, non-serious adverse events and adverse events of special interest (AESI) during the on-treatment period will be tabulated. The list of AESI will also include relevant events for spartalizumab, LAG525, capmatinib, canakinumab and ribociclib which will be defined in the SAP.

Project-specific AESI should be defined in the case retrieval strategy (CRS) with regular updates whenever necessary.

All deaths (on-treatment and post-treatment) will be summarized.

All AE, deaths and serious adverse events (including those from the pre and post-treatment periods) will be listed and those collected during the pre-treatment and post-treatment period will be flagged.

### **10.5.3.3 Laboratory abnormalities**

Grading of laboratory values will be assigned programmatically as per NCI Common Terminology Criteria for Adverse Events (CTCAE) v5. The calculation of CTCAE grades will be based on the observed laboratory values only, clinical assessments will not be taken into account.

CTCAE Grade 0 will be assigned for all non-missing values not graded as 1 or higher. Grade 5 will not be used.

For laboratory tests where grades are not defined by CTCAE v5, results will be categorized as low/normal/high based on laboratory normal ranges.

The following summaries will be generated separately for hematology, and biochemistry tests:

- Listing of all laboratory data with values flagged to show the corresponding CTCAE v5 grades if applicable and the classifications relative to the laboratory normal ranges

For laboratory tests where grades are defined by CTCAE v5

- Worst post-baseline CTCAE grade (regardless of the baseline status). Each subject will be counted only once for the worst grade observed post-baseline.
- Shift tables using CTCAE v5 grades to compare baseline to the worst on-treatment value

For laboratory tests where grades are not defined by CTCAE v5

- Shift tables using the low/normal/high/ (low and high) classification to compare baseline to the worst on-treatment value.

### **10.5.3.4 Other safety data**

#### **ECG**

12-lead ECG including PR, QRS, QT, QTcF, and RR intervals will be obtained for each subject during the study. ECG data will be read and interpreted centrally.

[figure not shown]
Categorical Analysis of QT/QTc interval data based on the number of subjects meeting or exceeding predefined limits in terms of absolute QT/QTc intervals or changes from baseline will be presented. In addition, a listing of these subjects will be produced by treatment group.

#### **Vital signs**

Data on vital signs will be tabulated and listed, notable values will be flagged.

### **10.5.3.5 Supportive analyses for secondary objectives**

Not applicable.

### 10.5.3.6 Tolerability

Tolerability of study treatment will be assessed by summarizing the number of dose interruptions, dose reductions, and permanent discontinuations of study treatments. Reasons for dose interruptions, dose reductions, and permanent discontinuations will be listed and summarized (see [Section 10.3](#)).

### 10.5.4 Immunogenicity

Immunogenicity will be characterized descriptively tabulating antidrug antibodies (ADA) prevalence at baseline and ADA incidence on-treatment.

The impact of ADA on the occurrence of safety endpoints, efficacy endpoints, [REDACTED] may be assessed as appropriate. Further details will be provided in the SAP.

### 10.5.5 Biomarkers

Changes in levels, phenotype and/or activation of T cell populations in the tumor and tumor microenvironment will be analyzed on an on-going basis. Every effort will be made to make this data available for decision making purposes. Such analyses may include, but are not limited to CD8+ T cell infiltration and T cell activation by IHC and gene expression analysis, and T cell repertoire/clonality by TCR-sequencing.

Biomarker-related hypotheses may be compared with results found in literature as well as verified with data derived from previous or concurrent clinical trials. [REDACTED]

[figure not shown]
There may be circumstances when a decision is made to stop sample collection, or not perform or discontinue the analysis of blood / fresh tumor biopsies due to either practical or strategic reasons (e.g., issues related to the quality and/or quantity of the samples or issues related to the assay). Under such circumstances, the number of samples may be inadequate to perform a rigorous data analysis and only the available data will be listed and potentially summarized.

#### 10.5.5.1 Outline of the data analysis

The proposed data analysis is aligned with the secondary biomarker objectives of the protocol. Several biomarker parameters ([Table 10-7](#)) will be periodically analyzed for each subject.

**Table 10-7 Parameter definitions for categorization of biomarker outcome at subject level**

Biomarker parameter	Analysis	Criteria for favorable biomarker result
Number of tumor infiltrating T cells (TIL)	Changes of CD8 + T cell numbers as assessed by IHC in tumor/ tumor microenvironment with treatment	Increase
Activation level of TIL	Change of T cell activation marker level(s) as assessed by IHC in tumor/tumor microenvironment with treatment	Increase
TIL repertoire/specificity of T cell response to tumor	TCR clonality changes as assessed by TCR-sequencing in tumor/tumor microenvironment with treatment	Increase

Biomarker parameter	Analysis	Criteria for favorable biomarker result
Changes in immune response gene expression signatures	Changes in expression of genes and/or gene signatures as assessed by mRNA analysis in tumor/tumor microenvironment with treatment	Defined per gene/gene signature

The following analyses may be used to determine the biomarker parameters for supporting the decision-making criteria to expand or not an arm in part 2:

- Assessment changes from baseline of the number of CD8+ T cells present in the tumor and/or tumor microenvironment for spartalizumab in combination with novel agents
- Assessment of changes from baseline of T cell repertoire/clonality in the tumor and/or tumor microenvironment as assessed by TCR sequencing when combining spartalizumab with novel agents
- Assessment of changes from baseline of T cell activation markers as assessed by IHC present in the tumor and/or tumor microenvironment as assessed by IHC when combining spartalizumab with novel agents
- Assessment of changes from baseline of mRNA levels for expression of genes and/or gene signatures corresponding to immune activation in the tumor and/or tumor microenvironment

The overall biomarker result for each subject will be formulated according to the available biomarker data and by determining if each parameter is favorable or not according to the indicated criteria in [Table 10-7](#). If an individual subject has two or more favorable parameters from [Table 10-7](#) then that subject will be considered to have a favorable biomarker profile. For each arm, the proportion of subjects with a favorable biomarker profile (pFBP) are then defined as the number of subjects with favorable biomarker profiles divided by the number of subjects enrolled into the arm which are included in the “paired” biomarker analysis set for that particular interim analysis. The “paired” biomarker analysis set include all subjects in the safety set with an evaluable baseline tumor biopsy sample and at least one post-baseline tumor biopsy sample with evaluable results for 2 or more biomarker parameters listed in [Table 10-7](#). If other biomarker data are available at the time of an interim analysis, these may also be considered. More details will be provided in the Statistical Analysis Plan or Biomarker Analysis Plan.

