### 7.2.3.1 Biomarker assessments in tumor tissue

In the non-randomized section of the study, mandatory screening tumor samples will be centrally assessed to determine LAG-3 status for enrollment into arm 1A.

For all arms (randomized or non-randomized), biomarker analyses in mandatory tumor samples to assess changes in levels, phenotype and activation of T cell populations in the tumor and tumor microenvironment will support the decision making at each interim analysis as a part of the secondary objectives (Table 3-1). Secondary objective biomarker analyses may include but are not limited to CD8+ T cell infiltration and T cell activation by IHC, gene expression analysis by Nanostring and/or T cell repertoire/clonality by TCR-sequencing [REDACTED]. Analyses will be performed on an on-going basis, such that the data will be readily available for decision making purposes at each interim analysis.

[REDACTED]

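### The favorable biomarker profile needs two favorable parameters out of however many were evaluable, so the proportion favorable (pFBP) rises with assay completeness and a value near 50% cannot be told from no effect

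*Protocol*

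**What the plan says.** Table 3-1 makes pFBP a secondary endpoint for all arms. Table 10-7 lists four parameters, with a column headed "Criteria for favorable biomarker result". For CD8+ T cell number, T cell activation level and TCR clonality, the entry is a single word asking for an increase. The clonality row, for example, analyses "TCR clonality changes as assessed by TCR-sequencing in tumor/tumor microenvironment with treatment". For gene expression the criterion is to be defined for each gene or signature.

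The paragraph after the table gives the subject-level rule:

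- What is used: "The overall biomarker result for each subject will be formulated according to the available biomarker data".
- The count: "If an individual subject has two or more favorable parameters from" the table, "then that subject will be considered to have a favorable biomarker profile".
- The denominator: the paired biomarker analysis set, which requires an evaluable baseline biopsy and "at least one post-baseline tumor biopsy sample with evaluable results for 2 or more biomarker parameters listed in" the table.

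The paragraph ends by leaving further detail to the SAP or Biomarker Analysis Plan.

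On use, Section 7.2.3.1 says that the biomarker analyses in the mandatory tumor samples "will support the decision making at each interim analysis as a part of the secondary objectives". Sections 4.2.1, 4.2.2 and 10.4.2 base the formal thresholds on confirmed ORR, with biomarker data considered alongside.

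**The concern.** The required count is fixed at two, while the number of parameters that can contribute varies from two to four. For a given subject, one more evaluable parameter can add to the favorable count but never reduce it. A subject with more completed assays is therefore more likely to be called favorable, whatever the drugs do. Three of the criteria are stated as a direction of change only, so measurement and sampling variation between two biopsies can satisfy them.

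Completeness may well differ across arms and over time. Section 7.2.3 lets the sponsor omit a collection or an analysis for practical or strategic reasons. Section 7.2.3.1.1 makes the tissue quality criteria for the baseline sample mandatory in the randomized arms but only recommended in arm 1A. In arm 1A (Section 7.2.3.1.2), other biomarkers are run on the tissue left after LAG-3 testing. Arms 1 and 1A receive the same drugs, so their pFBPs invite side-by-side reading.

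The protocol states no null or target value for pFBP, and there is no untreated arm against which to read it. At stake is how a secondary endpoint that feeds interim discussions can be interpreted.

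**Working it through.** The protocol gives no expected or null pFBP, so there is no figure of its own to reproduce.

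**Inputs from the protocol (Section 10.5.5.1 and Table 10-7).** Favorable if at least 2 parameters are favorable; k = 2, 3 or 4 evaluable; three criteria are an increase; the fourth is not specified.

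**Assumptions, not in the protocol.** With no drug effect, each parameter is favorable with probability p = 0.5. The gene-expression parameter is first given the same 0.5. Independence is assumed first, then relaxed.

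**Step 1: independent, p = 0.5.** P(at least 2 of k) = 1 − (1 − p)^k − k·p·(1 − p)^(k−1).

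- k = 2: 1 − 0.25 − 0.50 = 25%
- k = 3: 1 − 0.125 − 0.375 = 50%
- k = 4: 1 − 0.0625 − 0.25 = 68.75%

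**Step 2: correlated changes.** Take equally correlated normal changes centred at zero. At correlation 0.5 the number of rises is uniform on 0 to k, so the probability is (k − 1)/(k + 1), or 1/3, 2/4 and 3/5. Simulation with 1,000,000 subjects agrees:

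| Correlation | k = 2 | k = 3 | k = 4 |
|---|---|---|---|
| 0 | 25% | 50% | 69% |
| 0.3 | 30% | 50% | 63% |
| 0.5 | 33% | 50% | 60% |
| 0.7 | 37% | 50% | 57% |
| 0.9 | 43% | 50% | 54% |
| 1 | 50% | 50% | 50% |

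The 50% at k = 3 needs neither independence nor the gene-expression row. With the three increase-based parameters and no ties, either at least two rise or at least two fall. If flipping all signs leaves the joint distribution unchanged, each outcome has probability one half.

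**Step 3: gene-expression criterion met with probability q, the others 0.5, independent.**

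- k = 4: 53.8% (q = 0.10), 59.4% (q = 0.25), 78.1% (q = 0.75)
- k = 2 with gene expression as one of the two: 0.5 × q = 5.0%, 12.5%, 37.5%

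**Step 4: a rise less likely than a fall or tie, p = 0.40 for all, independent.**

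- k = 2: 0.4² = 16.0%
- k = 3: 3 × 0.4² × 0.6 + 0.4³ = 35.2%
- k = 4: 1 − 0.6⁴ − 4 × 0.4 × 0.6³ = 52.5%

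**Step 5: effect of completeness on an arm's pFBP (illustration).** Suppose half the subjects in one arm have three increase-based parameters evaluable instead of two. The no-effect pFBP then rises by 0.5 × (50 − 25) = 12.5 points under independence, or 0.5 × (50 − 33.3) = 8.3 points at correlation 0.5.

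**The case against.** The strongest reply is that Table 10-7 gives a direction, not a cut-off. Section 10.5.5.1 sends further detail to the SAP or Biomarker Analysis Plan, neither of which is at hand, so a minimum change per assay may be set there. This stands: the lack of a cut-off in the protocol is not itself a fault. It does not reach the two-of-available rule or the mixed denominator, which the protocol states in full.

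A reader might infer that any increase is favorable for every parameter, and that 25% to 69% of untreated-like subjects would qualify depending only on the number of assays. The protocol does not support that:

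- The gene-expression criterion is open, and the 69% gives it an assumed 50% chance.
- Independence is hard to defend for related T cell measures from the same paired biopsies. Correlation narrows the range toward 50%, and at correlation 1 the completeness effect disappears.
- Ties, or a chance of a rise below one half, lower every figure.

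A reader might also infer that arms could be expanded on noise. The formal rules rest on confirmed ORR, no threshold is attached to pFBP, and no formal between-arm comparison is planned. All four randomized arms have already been declared futile, so the remaining decisions concern arm 1A.

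Nor is it right that the trial cannot show T cell changes. Section 10.5.5.1 lists separate change-from-baseline assessments, Section 10.5.5.3.2 provides for listing and summarizing the biomarker data, and a very high pFBP would still be informative.

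**Conclusion.** The point holds for the rule that the protocol fixes: two favorable parameters out of however many are available, in a denominator that mixes subjects with two, three and four evaluable. Under a symmetric no-effect model, the chance of a favorable profile is 50% with the three increase-based parameters at any correlation. With only two of them it is 25% under independence and 33% at correlation 0.5. With four it is 69% or 60% respectively if the gene-expression criterion has a 50% chance, and about 54% under independence if that chance is 10%. These figures are illustrations under stated assumptions, not predictions, and a minimum change set elsewhere would lower them.

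A pFBP near 50% therefore cannot be distinguished from no effect on the protocol's wording, and pFBPs from arms or interim analyses with different assay completeness should not be compared. The consequence is limited to the reading of a supportive secondary endpoint; the ORR-based decision rules are unaffected.

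**What to change.** In Section 10.5.5.1, either compute pFBP only in subjects evaluable for the same named set of parameters, or report it separately by number of evaluable parameters. In both cases show the no-effect rate beside it, with the assumed chance of a rise, the correlation and the gene-expression criterion stated.

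If the SAP or Biomarker Analysis Plan does not already do so, set a minimum change for each assay before the arm 1A interim data are read. It should come from existing assay-reproducibility data. The mandatory biopsies are at screening and on treatment only, so this trial cannot supply untreated paired biopsies for the purpose.

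The change is to wording and tables and needs no new samples. The price is a smaller denominator or smaller strata and, with a minimum change, a lower reported pFBP.

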#### 10.5.5.2 Data handling principles

Data preprocessing and transformations will be described in detail in the Programming Dataset Specifications document.

[figure not shown]
#### 10.5.5.3 Data analysis principles

##### 10.5.5.3.1 Analysis sets

Unless otherwise specified, all statistical analyses of biomarker data will be performed on subjects with biomarker data (Biomarker analysis set).

##### 10.5.5.3.2 Basic tables, figures and listings

Unless otherwise stated, as project standard, all biomarker data collected will be listed and summarized. In the event of the collection of large biomarker data such as next generation sequencing, gene expression or protein expression panels, some pragmatic considerations

[figure not shown]
[figure not shown]

will be applied to limit output, as these may easily top thousands, if not tens of thousands of pages offering little to no scientific value.

Depending on the endpoint of interest, graphical displays such as box plots or strip plots may be used to assess the relationship of different biomarkers with clinical benefit. These may be separated by treatment arm and include either baseline or change from baseline values, where applicable.

For categorical markers such as mutation status, 2x2 contingency tables may be used to assess the relationship with clinical benefit and or Kaplan–Meier curves may be generated given the number of number of PFS events warrant such an assessment.

[figure not shown]
## **10.7 Interim analysis**

### **10.7.1 Randomized section of the study**

#### **Part 1: Selection phase**

As described in [Section 4.2.1](#), the first interim analysis is planned for ORR once at least ten subjects have been randomized into each of the three initial treatment groups (arm 1, arm 2, arm 3), and have either completed two post-baseline tumor assessments or have discontinued study treatment. Subsequent interim analyses will be conducted approximately every five months thereafter since that is the scheduled timeframe to have two post-baseline scans. The first interim analysis for arm 4 (ribociclib and spartalizumab) will be synchronized with the subsequent planned interim analyses for the other arms and will occur when at least 10 subjects have been randomized to that arm, and have either completed two post-baseline tumor assessments or have discontinued study treatment. Enrollment and assessment at subsequent interim analyses for each treatment group will continue until the criteria for futility or advancement into the expansion phase have been met, or 45 subjects have been randomized into a treatment group using decision rules presented in [Section 10.4.2.1](#).

Of note, interim analyses will continue to be performed in the randomized section of the study at the pre-defined frequency until a clinical decision (e.g. arm declared futile or efficacy probabilistic threshold crossed) on each arm in part 1 has been made. Even if declared futile, combination arms will be analyzed at subsequent interim analyses until all

subjects have been reported at least once (i.e. had a minimum follow-up of 20 weeks). Additional descriptive analyses may be performed if required.

## **Part 2: Expansion phase**

No formal interim analysis is planned for this part of the trial. The first primary analysis will be performed once the first expanded arm has fully enrolled and also after all patients randomized had at least 9 months of follow-up. This timing would allow for a potential minimum duration of response of 6 months for all subjects randomized. Formal hypothesis testing of the primary endpoint (as described in [Section 10.4.2.1](#)) will be performed at the primary analysis. The final analysis will be performed at the end of the study as described in [Section 4.3](#).

### **10.7.2 Non-randomized section of the study**

#### **Part 1 : Selection phase**

As described in [Section 4.2.2](#), there will be one interim analysis planned for ORR once all patients treated in arm 1A have either completed two post-baseline tumor assessments or have discontinued study treatment.

#### **Part 2: Expansion phase**

A 2nd interim analysis will be conducted once 40 patients have been treated within selection and expansion phases and have either completed two post-baseline tumor assessments or have discontinued study treatment. The primary analysis of this non-randomized section of the study will be performed once all patients treated in arm 1A had at least 9 months of follow-up. This timing would allow for a potential minimum duration of response of 6 months for all subjects enrolled. Formal hypothesis testing of the primary endpoint (as described in [Section 10.4.2.2](#)) will be performed at this primary analysis. The final analysis will be performed at the end of the study as described in [Section 4.3](#).

## **10.8 Sample size calculation**

### **10.8.1 Randomized section of the study**

In this section, sample size will be presented based on specific potential scenarios for true ORR in the first four combination arms evaluated. In particular, for selection phase (part 1), since one can consider a wide variety of potential true ORR scenarios, the sample size will not be based on an exact calculation leading to one fixed number, but will instead be characterized by simulation based on average number of subjects enrolled into these arms under each individual scenario for true ORR. It is important to emphasize that the true underlying efficacy activity (in terms of ORR) of the four initial arms will have a substantial bearing on the total sample size needed in part 1. Subsequently, and given the adaptive nature of the study design, the sample size needed in expansion phase (part 2) to ensure sufficient power will depend on the ORR observed in part 1 and in particular on the rate observed in the arm that qualifies for expansion to part 2.

The sample size calculation for parts 1 and 2 were performed using SAS 9.4 software, based on the probabilities of first determining a efficacious treatment and a futile (non-efficacious) treatment in the selection phase (part 1), and then determining the number of subjects needed

to reject the null hypothesis (part 2). The following assumptions were made in the estimation of the required sample size:

**Part 1: Selection phase:**

Simulation based determination of the sample size needed for part 1 considers the following:

- The interim analyses will be performed with frequency described in [Section 10.7.1](#).
- Decisions rules for declaring an efficacious or non-efficacious (futile) treatment described in [Section 10.4.2.1](#) are used at each of the interim analyses
- Considers at least two interim analyses for the first three arms before the initiation of an interim analysis for arm 4 (ribociclib + spartalizumab)
- Takes into account the actual randomization in the first three arms for the first interim analysis (13 subjects for arm 1 [LAG525 + spartalizumab], 10 subjects for arm 2 [capmatinib + spartalizumab], and 12 subjects for arm 3 [canakinumab + spartalizumab])
- Allows for a random allotment of subjects (between 10 and 16) in arm 4 before the first interim analysis is conducted for that arm. Random allotment is necessary since the timing of the first interim analysis in this combination arm is controlled by the timing of the previous interim analyses before this arm begins randomization.
- Enrolling a cap of 45 subjects for combination arms that cannot be selected either to be an efficacious or non- efficacious treatment.
- An accrual rate of 8 subjects per month
- 1000 simulations for each scenario of true ORR

Taking into account the efficacy/futility criteria discussed in [Section 10.4.2.1](#), below are results of simulations assuming a variety of scenarios for the ‘true’ underlying ORR. [Table 10-10](#) below presents average sample size (‘N’) along with percentages for declaring ‘futile’ and ‘promising/efficacious’ combination arms.

**Table 10-10 Simulation based sample size (N) with percentages for declaring ‘futile’ and ‘efficacious’ combination arms in the selection phase**

Scenario	Arm	True ORR	Avg. N	Futility %	Efficacious %
1	1	0.10	31.6	75.35	4.57
	2	0.10	25.8	75.55	8.63
	3	0.10	27.7	72.91	11.53
	4	0.10	30.6	74.10	7.06
2	1	0.10	31.5	75.11	4.51
	2	0.10	25.9	75.77	8.59
	3	0.10	27.7	72.92	11.74
	4	0.25	26.5	5.99	71.24
3	1	0.10	32.6	75.11	4.29
	2	0.25	23.7	7.45	73.91
	3	0.25	21.6	5.40	78.86
	4	0.25	26.5	5.52	71.67
4	1	0.25	28.1	4.82	71.07
	2	0.05	19.5	97.38	0.97
	3	0.07	25.8	89.85	4.90
	4	0.15	32.7	38.17	21.91
5	1	0.25	29.2	4.40	69.59

Scenario	Arm	True ORR	Avg. N	Futility %	Efficacious %
	2	0.30	20.3	2.94	89.50
	3	0.35	15.7	0.67	97.62
	4	0.25	26.6	5.66	70.84
6	1	0.17	34.2	26.73	28.70
	2	0.19	27.6	22.24	44.67
	3	0.18	27.4	23.11	46.05
	4	0.16	31.7	33.27	26.97

The simulation results for part 1 demonstrate that in an efficacious arm with the true ORR of, for example 25%, the sample size will be approximately 22-29 subjects. In an arm with even higher efficacy, e.g. ORR of 35%, the sample size will be approximately 16 subjects since this arm will have a higher likelihood of being stopped earlier and declared as efficacious. On the other hand, an arm that is clearly futile, e.g. an arm with the true ORR of 5%, the sample size will be approximately 20 subjects. Based on the simulations results presented in [Table 10-10](#), the expected average sample size in part 1 for all four arms together range between 92 and 121 subjects. The maximum sample size in part 1 for all four arms together is 180 subjects corresponding to the scenario when all four arms will be capped at 45 subjects.

The simulation results also demonstrate that decision rules described in [Section 10.4.2.1](#) are adequate to detect efficacious and futile arms with high probabilities. For example, an arm with the true ORR of 25% will be declared as efficacious with approximately 70-79% probability. Similarly, an arm with the true ORR of, for example, 10% will be declared as futile with probability of 73-76% and declared as efficacious with probability of 4-12%. Of note, the probabilities for efficacy and futility estimated for each scenario and each arm do not add up to 100% since there is a possibility for each particular row in the table that given arm will fail to satisfy either of the criteria and its enrollment will subsequently be stopped using the cap of 45 subjects. Further simulation results for the selection phase will be summarized in the SAP Technical Appendix.

